Study Objectives:	
 1. To evaluate and compare pathogen identification of children with musculoskeletal infections (MSKI) using Karius® plasma-based quantitative Next-Generation Sequencing Test (Karius Test) and standard culture methods. 2. To examine the kinetics of pathogen cell-free DNA (cfDNA) in the plasma of children with MSKI and compare the quantity of cfDNA to clinical symptoms and inflammatory markers, C-reactive protein (CRP), Erythrocyte sedimentation rate (ESR), and procalcitonin (PCT), a biomarker thought to be more specific for bacterial infections. 3. To evaluate whether samples quantitative cfDNA predicts severe disease in children with MSKI.
Study Design:	We will prospectively enroll children evaluated at Riley Hospital for Children (RHC) with musculoskeletal infections (osteomyelitis, septic arthritis, or pyomyositis) over a 12-24-month period. Eligible subjects will be identified by referral from the infectious diseases and orthopedic services at RHC. Subjects and their parent(s) or guardian(s) will be informed of the study and, upon providing informed consent, will be enrolled in the study. Study samples will be collected at time points that closely parallel clinical testing as performed during routine, standard care for treatment of MSKI. Immediately after enrollment, up to two detection blood samples will be obtained for real-time NGS testing at Karius Laboratory (Redwood City, CA) to determine if additional study samples will be obtained. Detection of a pathogen by NGS will be interpreted as a positive result that qualifies the collection of subsequent study samples. Pathogen identification by NGS will be compared to standard cultures methods, and quantitative cfDNA will be evaluated over time.
Duration of Study:	12-Month Period
Number of Sites:	1: Riley Hospital for Children
Sample Size:	38 Subjects

	Clinical Study Protocol
Title: Plasma-Based Next-Generation Sequencing for Pathogen Detection and Quantification in Children with Musculoskeletal Infections	
Supersedes: 0.8	Document Number: KDG-002 Clinicaltrials.gov #: NCT03846804
	Effective Date: 19Oct2021

Page: 9 of 30

1 BACKGROUND INFORMATION AND RATIONALE

1.1 Background Information

Musculoskeletal infections (MSKI; osteomyelitis, septic arthritis, and pyomyositis) are a common cause for hospitalization and, in children, among the most frequent type of invasive infection. Due to the risk of local tissue destruction and metastatic bacterial spread, MSKI require prompt diagnosis and targeted treatment. Current diagnostic modalities require isolation of a causative organism by culture from a sterile site (e.g., blood, bone or joint fluid); however, nearly half of all MSKI in children remain culture-negative [1,2,3]. Several reasons for this exist, including antibiotic use prior to obtaining a culture; lack of a surgical or drainage procedure; and the fastidious nature of certain organisms in culture [4]. Absence of a microbiologic diagnosis has significant ramifications on the management of children with MSKI, as patients are ultimately treated with broad, often multi-agent antimicrobial regimens to cover all likely causative pathogens.

1.2 Rationale for the Study

A culture-independent molecular test, such as the Karius® plasma-based next-generation sequencing (Karius Test) test, would not be prone to the aforementioned barriers and has the potential to increase pathogen detection allowing for targeted antimicrobial therapy.

Additionally, quantitative NSG has the potential to improve another component of the complex management of children with MSKI—length of therapy (LOT). Typically, length of therapy for MSKI in children is 2-6 weeks depending on the infection type and severity, however, variability in this practice exists [5,6]. Ultimately LOT is typically determined by clinical symptoms and inflammatory makers (e.g., C-reactive protein (CRP) and erythrocyte sedimentation rate (ESR)) at the end of the pre-determined timeframe. This approach, while often effective, is challenging in children given that the clinical exam can be unreliable and inflammatory markers are non-specific, often influenced by intercurrent illnesses or recent procedures. An objective assay with improved specificity, such as the Karius Test, which has the ability to quantitate cell-free pathogen DNA (cfDNA) and has been shown to correlate with clinical findings in other disease states [7], could allow for a tailored treatment approach and address an unmet need for children with MSKI.

Finally, the ability of the Karius Test to quantitate cfDNA has the potential to inform disease severity and potentially predict complications in children with MSKI. While numerous proposed strategies have been published to develop a prediction algorithm for disease severity in children with MSKI, each of these methods has significant limitations [8], and none involve quantification of cfDNA. If the Karius Test could be used to predict severe disease, it could have a significant impact on early management of this complex disease.

	Clinical Study Protocol	
	Title: Plasma-Based Next-Generation Sequencing for Pathogen Detection and Quantification in Children with Musculoskeletal Infections	
Supersedes: 0.8	Document Number: KDG-002 Clinicaltrials.gov #: NCT03846804	
	Effective Date: 19Oct2021	Page: 10 of 30

Taken together, the Karius Test has the potential to significantly impact antibiotic utilization and quality of care for children with MSKI. In this proposal, we seek to investigate the utility of this novel technology in children with MSKI.

2 STUDY OBJECTIVES AND ENDPOINTS

2.1 PRIMARY OBJECTIVES

- 1) To evaluate and compare pathogen identification of children with musculoskeletal infections using Karius plasma-based quantitative NGS test (Karius Test) and standard culture methods. We hypothesize that the Karius Test will have a high positive agreement for culture positive samples and increase pathogen detection in culture-negative infections.
- 2) To examine the kinetics of pathogen cell-free DNA (cfDNA) in the plasma of children with MSKI and compare the quantity of cfDNA to clinical symptoms and inflammatory markers, CRP, ESR, and procalcitonin (PCT), a biomarker thought to be more specific for bacterial infections. We hypothesize that the cfDNA quantity will correlate strongly with clinical symptoms as well as inflammatory markers (CRP, ESR and PCT).
- 3) To evaluate whether initial detection samples quantitative cfDNA predicts severe disease¹ in children with MSKI. We hypothesize that cfDNA quantity at admission will correlate with severe or complicated MSKI.

¹Severe disease defined by any of the following: need for intensive care unit (ICU) care, infection in two or more non-contiguous anatomic sites (disseminated disease), complicated disease (need for more than 1 debridement procedure, deep vein thrombosis [DVT] or thromboembolic disease, pathologic fracture)

2.2 EXPLORATORY OBJECTIVE

- 1) To evaluate and compare pathogen identification from synovial fluid of children with septic arthritis using Karius Test and standard culture methods.

2.3 PRIMARY ENDPOINT MEASURES

- 1) To evaluate and compare pathogen identification of children with musculoskeletal infections using Karius Test NGS and standard culture methods:
 - a. Describe pathogen identification by Karius Test vs. standard culture methods
- 2) To examine the kinetics of pathogen cell-free DNA (cfDNA) in the plasma of children with MSKI and compare the quantity of cfDNA to clinical symptoms and inflammatory markers, CRP, ESR, and procalcitonin (PCT), a biomarker thought to be more specific for bacterial infections.

	Clinical Study Protocol
Title: Plasma-Based Next-Generation Sequencing for Pathogen Detection and Quantification in Children with Musculoskeletal Infections	
Supersedes: 0.8	Document Number: KDG-002 Clinicaltrials.gov #: NCT03846804
	Effective Date: 19Oct2021 Page: 11 of 30

- a. Determine quantification of cf DNA in molecules per microliter (MPM) at each time point using the Karius Test.
- b. Determine CRP, ESR, PCT at each timepoint and compare to cfDNA MPM.

3) To evaluate whether initial detection sample quantitative cfDNA predicts severe disease in children with MSKI.

- a. Determine the correlation of cfDNA level in MPM to severity of infection (defined in SECTION 2.1)

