3 STUDY DESIGN

This is a prospective study of children 6 months to 18 years of age (inclusive) with the diagnosis of MSKI at Riley Hospital for Children (Indianapolis, IN) over a 12-month period. Eligible subjects will be identified by referral from the infectious diseases and orthopedic services at RHC. Subjects will be identified and screened for eligibility (Section 5.3) by the study team. Subjects and their parent(s) or guardian(s) will be informed of the study and, upon providing informed consent, will be enrolled in the study.

Study samples will be collected to coincide with routine clinical care. Samples will be collected when sufficient sample is available after routine care samples are obtained. Additional venipunctures specific for collection of study samples will be performed only with participant's consent.

Collection of NGS samples for real-time testing:

Detection samples will be collected prior to any surgical procedures and will be sent to Karius® Laboratory (Redwood City, CA) for real-time testing to determine if the pathogen is detected by NGS. Karius will notify the study team of the result(s). A positive result for any detection sample will qualify the collection of subsequent study samples. Detection samples will be collected within 96 hours of enrollment, and if applicable, 12-72 hours after the first sample, upon any re-admission for MSKI, or when prior detection sample results are inconclusive.

Collection of subsequent study samples

If NGS testing identifies a pathogen in the detection sample(s), subsequent study samples will, will be collected \geq 48 hours after previous sample collected. When the Detection NGS result(s)

Clinical Study Protocol	
Title: Plasma-Based Next-Generation Sequencing for Pathogen Detection and Quantification in Children with Musculoskeletal Infections	
Supersedes: 0.8	Document Number: KDG-002 Clinicaltrials.gov #: NCT03846804
	Effective Date: 19Oct2021
	Page: 12 of 30

is inconclusive or still pending, study samples may be collected at the appropriate timepoint(s). Collected sample(s) will be sent to Karius with qualifying result(s) from the Detection NGS sample(s). Up to 4 samples, including detection samples, will be collected per inpatient admission. (**Figure 1**)

[figure not shown]

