9 CLINICAL ADJUDICATION

9.2 Adjudication Process

NA

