9.3 Data Review

Upon the study completion, the comparison between Karius NGS testing and standard culture methods for pathogen identification will be reviewed by [name] and Karius. The study results will be summarized in a peer-reviewed publication.

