10 STATISTICAL CONSIDERATIONS

10.1 General Conditions for Statistical Analysis

Positive and negative agreement (percentage) will be used to compare culture and NGS for pathogen identification. Correlation between inflammatory markers and cfDNA quantification will be compared using Spearman's coefficient. Lastly, simple regression modeling will be used to assess the ability of cfDNA to predict severe disease.

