Culture Pathogen ID	Name of pathogen by culture
Culture source	Blood, bone/synovial fluid/tissue, both
NGS Pathogen ID- (IP1)	Name of pathogen by NGS
NGS Quantification- (IP1)	Molecule per microliter (MPM) of cfDNA
NGS Pathogen ID- (IP2)	Name of pathogen by NGS
NGS Quantification- (IP2)	Molecule per microliter (MPM) of cfDNA
NGS Pathogen ID- (IP3)	Name of pathogen by NGS
NGS Quantification- (IP3)	Molecule per microliter (MPM) of cfDNA
NGS Pathogen ID- (IP4)	Name of pathogen by NGS
NGS Quantification- (IP4)	Molecule per microliter (MPM) of cfDNA
NGS Pathogen ID- (OP1)	Name of pathogen by NGS
NGS Quantification- (OP1)	

	Clinical Study Protocol
	Title: Plasma-Based Next-Generation Sequencing for Pathogen Detection and Quantification in Children with Musculoskeletal Infections
Supersedes: 0.8	Document Number: KDG-002 Clinicaltrials.gov #: NCT03846804
	Effective Date: 19Oct2021

	Molecule per microliter (MPM) of cfDNA
NGS Pathogen ID- (OP2)	Name of pathogen by NGS
NGS Quantification- (OP2)	Molecule per microliter (MPM) of cfDNA
NGS Pathogen ID- (OP3)	Name of pathogen by NGS
NGS Quantification- (OP3)	Molecule per microliter (MPM) of cfDNA
WBC x 10 ³ /uL	White blood cell count
WBC Timepoint	(MM-DD-YYYY); 00:00
CRP	mg/dL
CRP Timepoint	(MM-DD-YYYY); 00:00
ESR	mm/hr
ESR Timepoint	(MM-DD-YYYY); 00:00
PCT	ng/mL
PCT Timepoint	(MM-DD-YYYY); 00:00

Clinical Study Protocol	
Title: Plasma-Based Next-Generation Sequencing for Pathogen Detection and Quantification in Children with Musculoskeletal Infections	
Supersedes: 0.8	Document Number: KDG-002 Clinicaltrials.gov #: NCT03846804
	Effective Date: 19Oct2021 Page: 29 of 30

Clinical Study Protocol	
Title: Plasma-Based Next-Generation Sequencing for Pathogen Detection and Quantification in Children with Musculoskeletal Infections	
Supersedes: 0.8	Document Number: KDG-002 Clinicaltrials.gov #: NCT03846804
	Effective Date: 19Oct2021
Page: 30 of 30	

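### Nothing in the plan keeps the culture reference independent of the NGS result, so positive agreement for primary objective 1 is open to bias

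*Combined protocol and SAP*

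**What the plan says.** - Section 2.1, objective 1, expects that "the Karius Test will have a high positive agreement for culture positive samples", and that NGS will add detections in culture-negative children. No figure is attached to high.
- Section 2.3(1a) gives the endpoint as "Describe pathogen identification by Karius Test vs. standard culture methods".
- Section 10.1 gives the statistic: "Positive and negative agreement (percentage) will be used to compare culture and NGS for pathogen identification". It gives no matching rule, interval or target.
- Section 3 sends detection samples for real-time testing and adds that "Karius will notify the study team of the result(s". The synopsis and Section 3 allow more than one detection sample, including a repeat after an inconclusive one.
- Section 4 leaves blood and source cultures to the treating physicians. The university clinical laboratory performs them; NGS is done at Karius.
- Appendix C has one culture entry, "Name of pathogen by culture", on the same form as the NGS organism for each sample. Section 10.2 lists the same single variable.
- Under "9.2 Adjudication Process" the whole entry is NA.
- Section 9.3 covers the final step: "Upon the study completion, the comparison between Karius NGS testing" and "standard culture methods for pathogen identification will be reviewed by [name] and Karius".
- In Section 10.5 the heading on missing, unused or spurious data has no readable text under it.

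**The concern.** Positive agreement needs a denominator (children with a culture pathogen) and a numerator (those in whom NGS named the same organism). Both need judgement when a culture grows a possible contaminant, when blood and source cultures differ, or when the two methods report at different taxonomic levels. The plan gives no readable rule for these cases, and the people who complete the form can already know the NGS answer.

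That knowledge can act in one direction. Calling an unmatched isolate a contaminant shrinks the denominator, and accepting a near match enlarges the numerator; both raise the figure. A child whose unmatched isolate is discarded also becomes culture-negative. If NGS had named another organism in that child, the discordance would then look like an added detection, which is the second half of the hypothesis. A reader of the published result could not tell how much of the agreement came from such decisions.

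**Working it through.** **1. The plan's own figure.** Section 10.4 expects at least 50 admissions and more than 75% participation: 50 × 0.75 = 37.5, rounded up to 38. The target reproduces. It rests on feasibility, and nothing below changes it.

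**2. Culture-positive children (assumption).** Section 1.1 says nearly half of these infections stay culture-negative. Taking 50% to 40% negative gives 38 × 0.50 = 19 to 38 × 0.60 = 22.8, so about 19 to 23 culture-positive children.

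**3. Effect of one decision.** Let x children match among n culture-positive, so positive agreement is x/n.
- One loose match accepted: (x + 1)/n − x/n = 1/n.
- One unmatched isolate dropped: x/(n − 1) − x/n = x/[n(n − 1)].

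The values of x are assumed, to cover starting agreement of about 70% to 90%.

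| n | x | x/n | one loose match | one isolate dropped |
|---|---|---|---|---|
| 19 | 13 | 68.4% | 73.7% (+5.3) | 72.2% (+3.8) |
| 19 | 15 | 78.9% | 84.2% (+5.3) | 83.3% (+4.4) |
| 19 | 17 | 89.5% | 94.7% (+5.3) | 94.4% (+5.0) |
| 23 | 16 | 69.6% | 73.9% (+4.3) | 72.7% (+3.2) |
| 23 | 18 | 78.3% | 82.6% (+4.3) | 81.8% (+3.6) |
| 23 | 21 | 91.3% | 95.7% (+4.3) | 95.5% (+4.2) |

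**4. Separating proper from improper removal.** Suppose 15 of 19 match. Of the other four isolates, two are true contaminants and one is a genuine low-virulence pathogen that NGS missed (all assumed). Intervals are exact (Clopper-Pearson) 95%.
- All isolates counted: 15/19 = 78.9% (54.4 to 93.9).
- Contaminants removed by a rule that ignores NGS: 15/17 = 88.2% (63.6 to 98.5).
- The missed pathogen dropped as well, because NGS did not match it: 15/16 = 93.8% (69.8 to 99.8).

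The step from 78.9% to 88.2% is legitimate. Only the step from 88.2% to 93.8%, one child and 5.5 points, is bias.

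**5. Range.** Steps 3 and 4 give 3.2 to 5.5 points per decision, so roughly 3 to 6. With no contaminants and no ambiguous matches there is nothing to decide and the effect is zero.

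**The case against.** A reader might infer that the investigator and the manufacturer settle pathogen and match status between them. The documents do not support that. Section 9.3 says the comparison is reviewed; it gives no power to reclassify. The reviewer's name is removed and that section states no role.

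A reader might also infer that Karius sees culture results while making its calls, or revises calls later. No text says either. The laboratories are separate, detection samples are tested in real time, and the joint review comes at study completion. The exposure lies in classification and matching, not in the assay.

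NA for adjudication can be read to mean that laboratory results are taken as issued, and the culture field may be no more than a short label mirroring the NGS one. Section 9 begins at 9.2 in the available text, so a lost 9.1 cannot be ruled out. The endpoint is descriptive and no threshold is set, so no pass or fail turns on a few points. The exact intervals are far wider than the shift.

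Most of this stands and limits the claim. It does not supply the missing safeguard. Even if results are taken as issued, a rule is needed for a contaminant, for discordant sources, and for which detection sample counts. The wide intervals describe sampling error; they do not cover a systematic shift in the estimate.

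**Conclusion.** The concern holds as a risk to the main figure for primary objective 1. The stated workflow combines real-time NGS results, one culture field on a shared form, no adjudication and an open final review. Nothing in the readable text makes the culture classification independent of the test being evaluated.

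The documents do not show that agreement will be inflated, and they do not allow the likely size to be estimated. The figure of roughly 3 to 6 points per affected child rests on 19 to 23 culture-positive children and starting agreement of about 70% to 90%, both assumed. The true effect may be zero. The change is worth making because it is cheap and because readers could not otherwise judge the result.

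**What to change.** In Section 2.3(1a), Section 9.3 and the case report form:

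1. Copy every culture isolate from the laboratory report. Class it as pathogen or contaminant by a written rule that uses only species, source and number of positive cultures, never the NGS result.
2. Name in advance which detection result counts, for example any conclusive detection sample from the index admission, with a rule for an inconclusive first sample. A rule tied to the first report alone would clash with the repeat samples that Section 3 allows.
3. Compute matches mechanically at species level, or at the lowest level the culture laboratory reports when it gives genus only, so that a genus-only report is not scored as discordant by default.
4. State that the review with Karius may comment on the comparison but may not reclassify isolates or matches.
5. Report positive agreement with exact 95% confidence intervals, and add a sensitivity line that counts all isolates.

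The cost is protocol wording and one extra form line per isolate. The target of 38 is unchanged and no extra samples or visits are needed. Positive agreement may come out slightly lower.

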2.4 EXPLORATORY ENDPOINT MEASURES

- 1) To evaluate and compare pathogen identification from synovial fluid of children with septic arthritis using the Karius Test and standard culture methods.
 - a. Describe pathogen identification by NGS of the synovial fluid compared to standard culture methods.

3 STUDY DESIGN

This is a prospective study of children 6 months to 18 years of age (inclusive) with the diagnosis of MSKI at Riley Hospital for Children (Indianapolis, IN) over a 12-month period. Eligible subjects will be identified by referral from the infectious diseases and orthopedic services at RHC. Subjects will be identified and screened for eligibility (Section 5.3) by the study team. Subjects and their parent(s) or guardian(s) will be informed of the study and, upon providing informed consent, will be enrolled in the study.

Study samples will be collected to coincide with routine clinical care. Samples will be collected when sufficient sample is available after routine care samples are obtained. Additional venipunctures specific for collection of study samples will be performed only with participant's consent.

Collection of NGS samples for real-time testing:

Detection samples will be collected prior to any surgical procedures and will be sent to Karius® Laboratory (Redwood City, CA) for real-time testing to determine if the pathogen is detected by NGS. Karius will notify the study team of the result(s). A positive result for any detection sample will qualify the collection of subsequent study samples. Detection samples will be collected within 96 hours of enrollment, and if applicable, 12-72 hours after the first sample, upon any re-admission for MSKI, or when prior detection sample results are inconclusive.

Collection of subsequent study samples

If NGS testing identifies a pathogen in the detection sample(s), subsequent study samples will, will be collected \geq 48 hours after previous sample collected. When the Detection NGS result(s)

Clinical Study Protocol	
Title: Plasma-Based Next-Generation Sequencing for Pathogen Detection and Quantification in Children with Musculoskeletal Infections	
Supersedes: 0.8	Document Number: KDG-002 Clinicaltrials.gov #: NCT03846804
	Effective Date: 19Oct2021
	Page: 12 of 30

is inconclusive or still pending, study samples may be collected at the appropriate timepoint(s). Collected sample(s) will be sent to Karius with qualifying result(s) from the Detection NGS sample(s). Up to 4 samples, including detection samples, will be collected per inpatient admission. (**Figure 1**)

[figure not shown]

Figure 1. Study Design- Samples for NGS testing will be collected to coincide with routine clinical care testing. Detection sample(s) sent for real-time NGS testing to determine if the Karius test identifies a pathogen. If a pathogen is detected by NGS, additional study samples will be collected throughout the treatment and follow up for MSKI.

Collection of Synovial Fluid from patients with septic arthritis:

When synovial fluid is obtained as part of routine medical care, excess or leftover synovial fluid may be collected and sent to Karius for potential NGS testing of the synovial fluid.

Procalcitonin:

A procalcitonin (PCT) level will be obtained at each study sample time point, along with routine clinical labs when sufficient sample can be collected.

If the Karius Test identifies an infectious agent in a clinically meaningful timeframe that may be of interest for the treating physician, [name], at his discretion, can contact the attending

Clinical Study Protocol	
Title: Plasma-Based Next-Generation Sequencing for Pathogen Detection and Quantification in Children with Musculoskeletal Infections	
Supersedes: 0.8	Document Number: KDG-002 Clinicaltrials.gov #: NCT03846804
	Effective Date: 19Oct2021

physician and notify them. [name] will stress that these results are from a research-use only test but will guide the treating physician to confirm the diagnosis with a commercially available CLIA-approved test.

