10.4 Determination of Sample Size

Based on current rates, it is estimated that at least 50 subjects will be admitted for MSKI at Riley Hospital for Children over a 12-month period. Based on an estimated >75% participation (consistent with similar previous studies) the target sample size of this study is 38.

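### Follow-up cfDNA is obtained only after a positive detection result, yet objective 2 is stated for all children with MSKI and the Spearman plan has no rule that keeps NGS-negative children in

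*Combined protocol and SAP*

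**What the plan says.** Every enrolled child is due at least one NGS test. The Study Synopsis states: "Immediately after enrollment, up to two detection blood samples will be obtained for real-time NGS testing at Karius Laboratory". Later samples depend on the result. Section 3 says "A positive result for any detection sample will qualify the collection of subsequent study samples", and the legend to Figure 1 repeats it: "If a pathogen is detected by NGS, additional study samples will be collected throughout the treatment and follow up for MSKI". Section 3 also allows samples to be drawn while a detection result is pending or inconclusive, but these go to the laboratory only once there is a qualifying result.

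Objective 2 in Section 2.1 concerns children with MSKI, with no restriction to those with detectable cfDNA: "We hypothesize that the cfDNA quantity will correlate strongly with clinical symptoms as well as inflammatory markers (CRP, ESR and PCT"). Section 2.3 sets the endpoint as MPM at each time point, compared with CRP, ESR and PCT at each time point.

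The analysis is in Section 10.1: "Correlation between inflammatory markers and cfDNA quantification will be compared using" Spearman's coefficient. Section 10.7 only points back to 10.1. In the text supplied, nothing follows the heading on missing, unused or spurious data in Section 10.5. The data set in Section 10.2 and the case report form in Appendix C ask for a pathogen name and an MPM value, and neither says what to enter for a negative test.

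**The concern.** Limiting follow-up to NGS-positive children is a sensible use of resources. The difficulty lies in the analysis. The condition for follow-up is the cfDNA result itself, so MPM and markers can be paired over time only in children selected on one of the two variables being correlated. At baseline the selection is avoidable, because negative children have also been tested. But a negative test yields no MPM, and Section 10.1 has no rule for it, so an analyst working from the data set could leave these children out without departing from the plan.

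This affects two things. The baseline coefficient, judged against a hypothesis of strong correlation, could come out too low because the children with least cfDNA are missing. And a kinetics result could be read as applying to all children with MSKI when it comes only from those with a positive detection result.

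**Working it through.** **1. The plan's own figure.** Section 10.4 gives at least 50 admissions and more than 75% participation: 50 × 0.75 = 37.5, rounded up to 38 ("the target sample size of this study is 38"). This reproduces. It is a feasibility count, and no target correlation, power or NGS detection rate is given. The detection rate d and the true correlation below are therefore assumptions.

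**2. Who has cfDNA data.** Baseline: all enrolled children with a valid detection sample. Follow-up: positives only, 38 × d. At d = 50% that is 19, at 80% about 30, at 90% about 34.

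**3. Baseline, one sample per child.** Take X (cfDNA) and Y (marker) as bivariate normal. For a true Spearman ρ the Pearson correlation is r = 2 sin(πρ/6), which is 0.518 for ρ = 0.50 and 0.618 for ρ = 0.60. Set the detection cut-off at the (1 − d) quantile of X. Compute Spearman (a) in children above the cut-off only, and (b) in all children, with those below it tied at the lowest rank. Large-sample simulation gives:

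| True Spearman | Detection | (a) Positives only | (b) Negatives tied lowest |
|---|---|---|---|
| 0.50 | 50% | 0.32 | 0.46 |
| 0.50 | 60% | 0.34 | 0.47 |
| 0.50 | 80% | 0.40 | 0.49 |
| 0.50 | 90% | 0.44 | 0.50 |
| 0.60 | 50% | 0.40 | 0.55 |
| 0.60 | 60% | 0.43 | 0.57 |
| 0.60 | 80% | 0.50 | 0.59 |
| 0.60 | 90% | 0.54 | 0.60 |

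Over 50 to 80% detection, dropping negatives costs 0.10 to 0.20 (for example 0.60 − 0.40 = 0.20). Keeping them as ties costs 0.01 to 0.05.

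**4. Serial samples pooled.** Assume four time points, between-child correlation 0.5, within-child SD 0.5, 60% detection, and later samples only if the first is above the cut-off. The middle column uses only data the design can yield: all visits of positives plus the baseline of negatives. The last column also needs follow-up samples from negatives, which the study does not obtain.

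| Fall per visit, cfDNA and marker | Positives only | Positives, plus negatives at baseline | All children, all visits, non-detects tied |
|---|---|---|---|
| none | 0.27 | 0.33 | 0.37 |
| 0.5 SD | 0.45 | 0.39 | 0.43 |
| 1 SD | 0.64 | 0.53 | 0.52 |

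Positives-only is lower with no trend and higher with a steep shared decline. Repeated samples from children whose cfDNA and markers both fall with treatment create correlation of their own, so the direction of the selection effect is not fixed.

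**5. Precision.** With standard error √[(1 + ρ²/2)/(n − 3)] on the Fisher z scale and an observed ρ of 0.50, n = 19 gives √(1.125/16) = 0.265 and a 95% interval of 0.03 to 0.79; n = 38 gives √(1.125/35) = 0.179 and 0.20 to 0.72.

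**The case against.** The strongest reply is that the plan contains no rule to discard negatives. Section 10.1 is silent, every enrolled child is tested, and a negative could be scored as zero. That stands. A reader might infer that only positive children are quantified and that the coefficient is attenuated as a matter of fact. The documents support neither: positivity is the condition for later samples, not for the first, and downward bias follows only at baseline and only if negatives are left out. Step 4 shows it cannot be asserted for pooled serial data.

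Second, a positives-only estimand for kinetics is legitimate, since cfDNA that was never detected has no decline to measure. That also stands; what is missing is the label.

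Third, ranking every enrolled negative lowest can overshoot. Section 5.3 requires only strong clinical suspicion and Section 9.2 marks adjudication as not applicable, so some negatives may not have MSKI. Assuming 10 to 20% of those enrolled are uninfected and NGS-negative, with markers 0.5 to 1.5 SD lower and 60 to 80% detection in the infected, a Spearman of about 0.48 among the infected became 0.45 to 0.60. This is a sound objection and it shapes the fix.

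Fourth, no numerical threshold defines a strong correlation, and at 19 to 30 positives the sampling SD (about 0.15 to 0.21) is as large as or larger than most of the loss. So no formal decision rule changes. But the loss is systematic and avoidable, and dropping negatives also widens the interval.

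**Conclusion.** The point holds as a mismatch between the population named in objective 2 and the population that can supply serial cfDNA, together with a missing rule for negative results. That much rests on the text alone.

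The size is conditional. If negatives are omitted at baseline, with 50 to 80% detection, one sample per child and bivariate normality, the Spearman coefficient falls by 0.10 to 0.20 from a true value of 0.50 or 0.60, and most of that is recovered by keeping negatives as tied lowest ranks. Detection rate and true correlation are assumed; the documents give neither. For pooled follow-up data no direction of bias is claimed. The change should be made before analysis, but the study remains sound without new data.

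**What to change.** Amend Section 10.1 as follows.

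1. **Baseline correlation.** Use one detection sample per child, with the choice fixed in advance where two exist (for example the first valid one). Include all enrolled children with a valid detection sample, available markers and a final MSKI diagnosis, taken from the infection type on the case report form. Rank NGS-negatives as tied lowest. Give positives-only and all-enrolled versions as sensitivity analyses. The form offers three infection types and no entry for a child in whom MSKI was not confirmed, so state how that child is recorded.
2. **Follow-up.** Report correlations and kinetics separately from baseline, labelled as in children with a positive detection NGS result, and limit the objective 2 kinetics conclusion to them. Use a within-child or clustered method, since each child contributes several samples.
3. **Table.** Show baseline CRP, ESR and PCT by NGS result, with the number missing.

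The cost is a little more analysis, one table and a narrower kinetics claim. Some children will still lack markers: Section 3 makes PCT depend on sufficient sample, and Section 4 leaves CRP and ESR to the treating physicians.
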